Analyses of mean change from baseline in continuous vital signs variables which are measured longitudinally were performed (systolic blood pressure, diastolic blood pressure, heart rate, weight, and temperature). For each change from baseline analysis, the following summary statistics were presented: sample size, baseline mean, visit mean, and the mean, standard deviation, and minimum/maximum of the changes from baseline. The baseline and visit means were calculated for each visit for subjects who have both a baseline and visit value.

Assessment of Potentially Clinically Significant Vital Signs Values

For selected vital signs variables, a listing of all observations collected was generated for subjects that had at least one post-baseline observation meeting pre-defined criteria for potentially clinically significant values. The number and percentage of subjects who have at least one post-baseline observation meeting the pre-defined criteria for potentially clinically significant values was provided for each variable.

Pre-defined criteria for potentially clinically significant vital signs values are given in Table 4 below based on CTCAE criteria:

Table 4. Criteria for Potentially Clinically Significant Laboratory Values – Vital Signs Variables

Vital Signs Variables	Criterion	Definition of Potentially Clinically Significant
Systolic blood pressure	High	Value > 150 mmHg
Diastolic blood pressure	High	Value > 100 mmHg
Heart Rate	Low	Value \leq 50 bpm
	High	Value \geq 120 bpm
Temperature	Low	Value \leq 36°C
	High	Value \geq 38.5°C

Analysis Conventions

Definition of Baseline

The baseline value was defined as the last non-missing measurement collected before the first dose of navitoclax.

Definition of Final Observation

The final observation (Final Visit) was defined as the last non-missing observation collected within 30 days following the last dose of navitoclax.

Definition of Rx Days (Days Relative to the First Dose of navitoclax)

Rx Days were calculated for each time point relative to the first dose date of navitoclax. They were defined as the number of days between the day of the first dose of navitoclax and the specific time point. Rx days were negative values when the time point of interest was prior to the first navitoclax dose day. Rx days were positive values when the time point of interest was after the first navitoclax dose day. The day of the first dose of navitoclax was defined as Rx Day 1, while the day prior to the first navitoclax dose was defined as Rx Day -1 (there is no Rx Day 0).

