This study will determine the dose limiting toxicity (DLT), the maximum-tolerated dose (MTD), and will assess the safety, pharmacokinetics, and preliminary efficacy of ABT-263 in subjects with relapsed or refractory CLL. ABT-263 will be administered orally under two different dosing schedules (14/21 day dosing schedule and 21/21 day continuous dosing schedule). The following 14/21 dose levels have been completed to date: 10 mg, 110 mg, 200 mg, and 250 mg. The following 21/21 dose levels have been completed to date: 125 mg, 200 mg, 250 mg and 300 mg.

Considering the coronavirus (COVID-19) pandemic, the benefit and risk to subjects participating in this study has been re-evaluated. Subjects receiving ABT-263 may be at an increased risk for COVID-19 infection or experience serious illness if infected. Management of these adverse events will be made on a case-by-case basis with consideration of benefit/risk. However, based on the population and disease being studied, and the anticipation that COVID-19 related risks are not expected to differ substantially between study subjects and the broader population of subjects receiving treatment for CLL, no change to the benefit/risk balance for subjects in this study is expected.

A detailed discussion of the preclinical toxicology, metabolism, and pharmacology can be found in the Investigator's Brochure.¹⁴

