Adjustments to the dose escalation schedule may also be made based upon preliminary pharmacokinetic and safety data obtained from concurrent dose escalation studies that are being conducted with ABT-263. These decisions will be based on the judgment of the AbbVie Medical Monitor in consultation with the investigator.

Subject assessments for safety and clinical progression will continue weekly through the first 2 cycles (6 weeks). Subsequently, subject assessments for safety and clinical progression will be performed once every cycle (every 3 weeks) or more frequently, as needed.

Phase 1 -14/21 Day Dosing

ABT-263 will be administered for 14 consecutive days followed by 7 days off drug to complete a 21-day cycle. Subjects will be instructed to self-administer ABT-263 orally once daily (QD) within 30 minutes after the completion of breakfast.

Figure 3. ABT-263 Dosing Schematic – Phase 1

Additionally, a continuous dosing regimen will be evaluated and compared to the 14/21 cyclic dosing regimen.

Phase 1 – 21/21 Day Continuous Dosing

Once either the MTD is defined or dosing in the 4th dose level is completed for the 14/21 day dosing schedule, whichever occurs first, a continuous dosing schedule will be assessed. Dosing with ABT-263 under the continuous dosing schedule (21/21 day) will begin at the dose estimated to provide exposure equivalent to the highest dosing level cleared (4th dose level) or the MTD from the 14/21 day schedule. For example, if the highest dose level cleared or the MTD from the 14/21 day dosing schedule is 375 mg, the continuous starting dose (defined Cycle 1 Day 1 dose) would be $(375 \times 14)/21$ or 250 mg. A minimum of three subjects will be enrolled in each cohort. The ABT-263 dose will be

escalated using a modified CRM as described previously for the 14/21 day regimen (Figure 2).

Prior to beginning the assigned 21/21 day continuous dosing regimen, a 7-day lead-in dose titration period will be implemented. In preclinical experiments in which stepwise increases in ABT-263 doses were administered to dogs every one or two weeks, the thrombocytopenic effect of higher doses was significantly attenuated. These data combined with the clinically observed rebound in platelet counts from nadir during continued ABT-263 dosing suggest that a lead-in period may help reduce the depth of the initial platelet nadir and provide an additional margin of safety.

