For subjects who participated in the Phase 1, 14/21 day dosing portion of the study, an analysis was performed on pharmacokinetic variables for Cycle 1 Day 1 dose to simultaneously explore for demographic variables that explained some of the variability in pharmacokinetics and to address questions of dose proportionality and linear kinetics. An analysis was performed for dose-normalized C_{max} , T_{max} , and dose-normalized AUC_t (AUC_{0-24}). The model used for the statistical analyses included dose level. This was done by classifying subjects by dose level. Covariates such as age, body weight, BSA, gender, and formulation, as well as others that might have explained some of the variability in the population, were considered for inclusion in the model initially. However, a covariate was dropped from the model if the regression coefficient was not significant at level 0.10. The natural logarithmic transformation was employed for C_{max} and AUC_t . Within the framework of the model, tests that had good power for a trend with dose were performed on the effect of dose level.

A corresponding analysis was also performed on pharmacokinetic variables of the dose on Cycle 1 Day 14 for both the Phase 1, 14/21 and 21/21 day dosing schedules. The variables included dose-normalized C_{max} , T_{max} , and dose normalized AUC_t (AUC_{0-8}).

Exploratory Efficacy

The following exploratory efficacy analyses were performed for Phase 1 and Phase 2 of the study. Unless specified otherwise all the analyses were presented by dose levels and overall; all the response and associated data were evaluated based on NCI WG Criteria (1996), and updated IWCLL NCI WG Criteria (2008) for Phase 1, and 2, respectively.

Progression-Free Survival

The distribution of PFS was estimated using Kaplan-Meier methodology. Median time to PFS and the corresponding 95% confidence interval were estimated.

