All analyses involving AEs were treatment-emergent adverse events (TEAE) only, unless otherwise specified. TEAE were defined as any event with onset after the first dose of navitoclax and no more than 30 days after the last dose of navitoclax. Events where the onset date was the same as the navitoclax start date were assumed to be treatment-emergent, unless the navitoclax start time and the AE start time were collected and the AE start time was prior to the navitoclax start time. If an incomplete onset date was collected for an AE, the AE was assumed to be treatment-emergent unless there was evidence that confirms that the AE was not treatment-emergent (e.g., the AE end date was prior to the date of the first dose of navitoclax).

Adverse event data was summarized and presented using primary MedDRA system organ classes (SOCs) and preferred terms (PTs) according to the MedDRA 22.0 coding dictionary.

The number and percentage of subjects experiencing treatment-emergent adverse events was summarized by phase 1 or 2, day cycle (14/21 or 21/21), navitoclax dose and for the whole portion of the study for the following adverse event summaries:

- Overview of treatment emergent adverse events
- Any treatment-emergent adverse event by System Organ Class and Preferred Term.
- Subject number associated with treatment-emergent adverse event.
- Treatment-emergent adverse events by System Organ Class, Preferred Term, and maximum NCI toxicity grade (CTCAE V3.0).

- Treatment-emergent adverse events broken down by maximum relationship to study drug.
- Any treatment-emergent NCI toxicity (CTCAE V3.0) grade 3 or 4 adverse events.
- Any treatment-emergent NCI toxicity (CTCAE V3.0) grade ≥ 3 adverse events.
- Treatment-emergent adverse events broken down by possibly or probably drug-related NCI toxicity grade ≥ 3 adverse events
- Treatment-emergent adverse events broken down by possibly or probably drug-related NCI toxicity grade 3 or 4 adverse events
- Any treatment-emergent adverse event with possibly or probably drug-related.
- For treatment-emergent serious adverse events, analyses similar to TEAE were provided.
- Any treatment-emergent adverse event leading to discontinuation of each drug.
- Any treatment-emergent adverse event leading to each drug interruption.
- Any treatment-emergent adverse event leading to each drug reduction.
- Any treatment-emergent adverse event leading to each drug delay.
- Any treatment-emergent adverse event leading to death.

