- Subject deaths occurring ≤ 30 days after last dose of study drug.
- Subject deaths occurring > 30 days after last dose of study drug.
- Any treatment-emergent DLT adverse events by primary MedDRA system organ class and preferred term.

Selected Adverse Events

Analysis of adverse events of safety areas of interest were conducted through the summary of MedDRA preferred terms identified using standard MedDRA queries (SMQs) and custom searches. Like TEAEs analyses, overview of selected AEs, and selected AEs by primary MedDRA system organ class and preferred term were provided. The search criteria for each of the safety areas of interest were described below.

Identified Risks

Thrombocytopenia - PTs: 10043554 Thrombocytopenia; 10035528 Platelet count decreased

Neutropenia - PTs: 10001507 Agranulocytosis; 10016288 Febrile neutropenia; 10029354 Neutropenia; 10059482 Neutropenic infection; 10049151 Neutropenic sepsis; 10029366 Neutrophil count decreased

Lymphopenia - PTs: 10025327 Lymphopenia; 10025256 Lymphocyte count decreased

Potential Risks

Hemorrhagic Events - SMQ 20000038 Hemorrhages (Narrow)

Opportunistic Infections - SMQ 20000235 Opportunistic Infections (Broad)

Tumor Lysis Syndrome - SMQ 20000219 Tumor Lysis Syndrome (Narrow)

Hepatotoxicity - SMQ 20000006 Drug Related Hepatic Disorders – Comprehensive (Broad); SMQ 20000007 Drug Related Hepatic Disorders – Severe Events Only (Narrow)

Increased Pancreatic Enzymes - SMQ 20000022 Acute Pancreatitis (Narrow)

Cardiovascular Events - SMQs: 20000004 Cardiac Failure (Narrow); 20000130 Pulmonary Hypertension (Narrow)

Venous Thromboembolic Events - SMQ 20000084 Embolic and Thrombotic Events, Venous (Narrow)

Cerebellar Hypoplasia - PT 10008033 Cerebellar Hypoplasia

Decreased Spermatogenesis - SMQ 20000210 Fertility Disorders (Narrow; males only)

Skin Cancer or Second Malignancies - SMQs: 20000173 Skin Neoplasms, Malignant and Unspecified (Broad); 20000090 Malignancies (Broad)

Allergic Reactions - SMQ 20000021 Anaphylactic Reaction (Broad)

Drug Interactions - HLT 10022528 Interactions

Analysis of Laboratory and Vital Signs Data

The value for baseline used in laboratory and vital sign analyses is defined in the Definition of Baseline section. All laboratory and vital signs were summarized by dose and the study portion as a whole.

Analysis of Mean Changes from Baseline in Clinical Laboratory Data

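### The SAP groups Phase 1 efficacy, laboratory and vital-sign results by dose without naming schedule, so as written the 200 mg and 250 mg rows merge 14/21 and 21/21 subjects

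*SAP*

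**What the plan says.** The SAP (16.1__9.1) has three display rules that bear on Phase 1.

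- Exploratory Efficacy: "Unless specified otherwise all the analyses were presented by dose levels and overall".
- Analysis of Laboratory and Vital Signs Data: "All laboratory and vital signs were summarized by dose and the study portion as a whole".
- Analysis of Treatment-Emergent Adverse Events: the number and percentage of subjects "was summarized by phase 1 or 2, day cycle (14/21 or 21/21), navitoclax dose and for the whole portion of the study".

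Only the third names schedule. The Cycle 1 Day 14 pharmacokinetic analysis is done "for both the Phase 1, 14/21 and 21/21 day dosing schedules".

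Protocol section 3.0 lists the doses given on each schedule: "The following 14/21 dose levels have been completed to date: 10 mg, 110 mg, 200 mg, and 250 mg" and "The following 21/21 dose levels have been completed to date: 125 mg, 200 mg, 250 mg and 300 mg". Section 5.1 says: "Additionally, a continuous dosing regimen will be evaluated and compared to the 14/21 cyclic dosing regimen". Section 4.0 makes determination of both the recommended Phase 2 dose and its schedule a Phase 1 objective. No section gives an endpoint or method for comparing the schedules.

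**The concern.** The two schedules are different interventions. One has a 7-day break in each cycle. The other is continuous and preceded by a lead-in. A programmer who follows the by-dose rules would produce one 200 mg row and one 250 mg row, each combining both. The adverse-event rule lists schedule and dose as separate classifiers, so in the SAP's own usage dose does not carry schedule with it.

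A merged row cannot show response, disease control or PFS for either regimen at that dose. By-visit laboratory means also lose a clear interpretation, because the same visit label falls on treatment under one schedule and in the drug-free week under the other. On any reading, the Phase 1 overall column mixes schedules and no total is provided for each schedule alone.

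**Working it through.** **Inputs.** Dose lists from Protocol 3.0; dosing days per cycle and minimum cohort size from 5.1; conversion between schedules from 5.1 and 5.6.4; platelet days from the platelet-count footnotes to Tables 1 and 2; 29 Phase 1 subjects from the SAP, Data Sets Analyzed.

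**1. The protocol's own conversion.** Continuous dose of equivalent exposure = 14/21 dose × 14/21. For the protocol's example, 375 × 14/21 = 250 mg, which reproduces the stated figure. By the protocol's own reckoning, equal milligrams on the two schedules are not equal exposure.

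**2. Overlap of the dose lists.**
- 14/21: 10, 110, 200, 250 mg.
- 21/21: 125, 200, 250, 300 mg.
- Shared: 200 and 250 mg.
- Schedule-by-dose groups: 4 + 4 = 8. Distinct doses: 8 − 2 = 6.

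Two of the six dose rows are affected. The other four each come from one schedule.

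**3. Planned drug per 21-day cycle** (dose × dosing days, leaving out the lead-in).

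| Dose | 14/21 | 21/21 | Ratio |
|---|---|---|---|
| 200 mg | 200 × 14 = 2,800 mg | 200 × 21 = 4,200 mg | 1.5 |
| 250 mg | 250 × 14 = 3,500 mg | 250 × 21 = 5,250 mg | 1.5 |

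On the protocol's scale, 200 mg on 14/21 corresponds to 200 × 14/21 = 133 mg continuous, and 250 mg to 250 × 14/21 = 167 mg continuous.

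**4. What a visit label means.** Platelets are scheduled on Cycle 1 Day 16 under both schedules. On 14/21 the last dose of the cycle is on Day 14, so Day 16 is off drug; on 21/21 it is on drug. The Cycle 2 Day 1 pre-dose value follows 7 drug-free days on 14/21 and uninterrupted dosing on 21/21. The SAP summarises mean change at each scheduled post-baseline visit, so in a merged row these values are averaged together.

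**5. Size of the merged rows.** Subjects per cohort are not given. Assume only these eight cohorts, each with at least 3 of the 29 subjects.
- Minimum used: 8 × 3 = 24, leaving 29 − 24 = 5 to place.
- One merged row: from 2 × 3 = 6 to 29 − 6 × 3 = 11 subjects.
- Both merged rows together: from 4 × 3 = 12 to 29 − 4 × 3 = 17 subjects.

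Under that assumption, between 12 and 17 of the 29 Phase 1 subjects would sit in rows that mix schedules.

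**6. Precision after splitting.** With 3 subjects and 1 response, the exact 95% interval is 0.8% to 90.6%. Merging does not rescue precision: 3 of 6 gives 11.8% to 88.2%. Either way the display is descriptive.

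**The case against.** The strongest reply is that the text never says the schedules are merged. Protocol 3.0 lists dose levels separately for each schedule, so the efficacy rule could mean the eight cohorts. That reading is open for efficacy, and to that extent the rule is ambiguous rather than wrong. It is much weaker for laboratory and vital-sign data, where the rule says only dose.

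Second, the SAP breaks no protocol commitment. Protocol 8.1.3 limits efficacy analyses to Phase 2a, and 8.1.4 asks for Phase 1 Cycle 1 summaries by dose. This is correct. But the SAP extended efficacy to Phase 1 and added schedule for adverse events, so it needs to define the grouping for the rest.

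Third, little turns on it. The 21/21 cohorts opened only after 14/21 reached its MTD or fourth dose level, so any contrast is sequential and non-randomised. Groups are tiny, subjects could escalate or switch, and the Phase 2a regimen had already been chosen. All of this stands: it limits what split tables can show, but does not justify merging two regimens.

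A reader might go further and infer three things that the documents do not support.

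- *That the protocol's comparison of schedules is lost.* Adverse events, including DLTs, are split by schedule, and the Day 14 PK analysis covers both. The protocol defines the recommended Phase 2 dose by DLTs and/or the MTD, and names no efficacy, laboratory or vital-sign comparison.
- *That the dose-limiting platelet effect is hidden.* The maximum-grade shift tables take each subject's worst post-baseline grade whatever the visit, and subjects with Grade 3 to 4 values are listed. Nadirs therefore remain visible.
- *That Cycle 1 Day 1 platelet means set untreated values against a fall of about 60%.* On 14/21 the pre-dose value that day is the baseline, not a post-baseline result. The 60% is a mean maximal drop with recovery, and 21/21 subjects reach that day only with counts of at least 50,000/mm³ that are stable or rising.

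**Conclusion.** The point holds in limited form. For laboratory and vital-sign data, and on the plain reading for efficacy, the stated grouping omits schedule although the adverse-event grouping includes it. As written, the two shared doses out of six distinct doses become rows that mix regimens differing 1.5-fold in planned drug per cycle, and by-visit means combine off-drug or just-after-off-drug 14/21 values with on-drug 21/21 values. The overall column mixes schedules on either reading.

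The consequence is confined to Phase 1 efficacy and to by-visit laboratory and vital-sign summaries. The 1.5 ratio is nominal: it assumes full planned dosing and leaves out the lead-in. The count of 12 to 17 subjects rests on the cohort assumption in the working. This should be corrected, but it does not call the chosen dose or schedule into question.

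**What to change.** In the SAP, for Phase 1 efficacy, laboratory and vital-sign tables, replace the by-dose grouping with assigned schedule (14/21 or 21/21) and assigned dose, giving eight groups instead of six. Add a total for each schedule and one for Phase 1 overall. This extends the schedule-and-dose classification already used for adverse events.

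Protocol 5.1 lets Phase 1 subjects escalate dose and later switch to the Phase 2a schedule, and the SAP does not say how such subjects are classified in these tables. State that they stay in their initially assigned schedule and dose group, and flag any response first met after a change of dose or schedule.

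The cost is SAP wording and a re-run of existing tables with a schedule variable that the adverse-event tables already require. The drawback is smaller cells at 200 and 250 mg. The tables should say that between-schedule differences are descriptive only.
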